Upon consent, participants will be randomly assigned to Group #1 or Group #2. The study design is akin to a waitlist control design, with group #1 (treatment group) receiving 8 weeks of intervention followed by 8 weeks of continued use of TLC intervention tools, and group #2 (waitlist group) doing respite as usual for 8 weeks, followed by 8 weeks of more intensive coaching from the TLC intervention. Both group #1 and #2 will fill out daily/weekly reviews of their respite use throughout the calendar functions of the TLC intervention tools during the 16-week intervention period, as well as monthly questionnaires at baseline/enrollment, week 4, week 8, week 12, week 16, and week 20.

Note: when we created the online, self-administered version of the TLC intervention, we merged all data collection instruments with intervention prompts into a single online delivery package, so both group #1 and group #2 receive access to the TLC study tools from day 1 and end their access at the end of week 20. This has altered the traditional "waitlist" (i.e., no contact) condition associated with group #2. Both group #1 and group #2 receive the same instructions and orientation to the study on day 1. The groups differ only in the amount and type of "virtual coaching" (instructions and prompts from the TLC website) they receive at week 1 and week 9. Group #1 receives more intensive coaching at week 1, with an encouragement to continue doing it on their own at week 9. Group #2 receives less intensive coaching at week 1, with a more intensive coaching instructions presented to them at week 9.

Self-administered questionnaires and daily ecological momentary assessments (EMAs). Participants in both conditions will complete self-administered questionnaires at baseline, and then every 4 weeks thereafter (for a total of 6 questionnaires, spread across 20 weeks). All questionnaires will be distributed electronically via email. Responses will automatically be recorded in a secure REDCap data base.

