Because this is part of early-stage intervention development activities (Stage 1), we have designed a clinical trial to pilot-test feasibility as well as efficacy of the redeveloped TLC intervention. We propose to use a waitlist control cohort design, using a fully powered sample to provide the most rigorous analysis possible. The waitlist design allows all participants to receive the intervention. As shown here in the figure, participants will be randomized to one of two sequences. After baseline data collection and an initial orientation/control period for the first 4 weeks, Group A will have 8 weeks of TLC intervention, then 8 weeks of follow-up. Group B will have 8 weeks of waitlist control, and then TLC intervention for 8 weeks, beginning at week 12. We will use ecological momentary assessment (EMA) during the entire 20-week study period to capture daily time-use trends for any respite periods received (n=140 daily reports, max). EMA aims to minimize recall bias and maximize ecological validity. Primary outcomes data will be collected via electronically administered surveys at baseline (T0) and every 4 weeks thereafter (T4, T8, T12, T16, T20), for a total of 6 assessments. This randomized, prospective, and longitudinal design

allows each participant to serve as its own control and offers opportunities to assess both within- and between-group differences over time (Group A vs. B).

Measures

The primary outcome is wellbeing, measured with two standardized scales indicating “caregiver burden” and “anxiety.” The mechanism driving the intervention effect is theorized to be related to respite time-use and time-use satisfaction. This construct is measured with “experienced” and “evaluative” time-use measures.

Analysis

The analysis to test for efficacy will specifically look at treatment x time interaction that combines both vertical (between individuals at given timepoints) as well as horizontal (evolution within individual over time) comparisons. We will utilize a multilevel model that consists of level 1 (within person) and level 2 (between person). Thus, the overall composite two level Multi-Level Mixed effects Model (MLM) is defined as follows with the first set of brackets representing fixed effects and second set random effects:

$$Y_{ij} = [\beta_0 + \beta_1 T_j + \beta_2 X_{ij}] + [\zeta_{0i} + \zeta_{1i} T_{ij} + \epsilon_{ij}] \quad [\text{equation 1}]$$

[figure not shown]

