where Y_{ij} is the outcome measure (Caregiver Burden and Anxiety) for participant (i) at time (j) where j is an indicator for time (baseline, 4 weeks, 8 weeks, 12 weeks, 16 weeks and 20 weeks). β_0 is the population mean level of the outcome measure prior to the TLC intervention, β_1 fixed effect for time independent of intervention, X_{ij} is the intervention status (pre-TLC or Post-TLC/Follow-up) at timepoint j, and β_2 is the intervention treatment effect. Random effects include individual-level intercept (ζ_{0i}), individual-level slope of change over time ($\zeta_{1i} T_{ij}$), and ϵ_{ij} for residual error of each outcome measure. Our hypotheses for Aim 2 are summarized here:

Over time, we expect intervention engagement to produce more positive wellbeing, with time satisfaction as the mechanism through which TLC achieves its effect.

- H1:** Burden & anxiety will be lower among the treatment group compared to those in control/waitlist condition (direct effect)
- H2:** Time-use satisfaction will be higher among the treatment group compared to those in control/waitlist (direct effect)
- H3:** Higher time-use satisfaction will be associated with lower burden & anxiety (direct effect)
- H4:** Higher time-use satisfaction will mediate the effect of the intervention on burden and anxiety (direct & indirect effect)

H1: Burden & anxiety will be lower among the treatment group compared to those in control/waitlist condition (direct effect)

Figure 2: Anticipated results for Wellbeing with TLC

Our primary outcome will test the hypothesis that there will be significant change in “caregiver burden” or “anxiety” immediately post intervention. Figure 2 shows the anticipated results with no change during the run-in period, increase in wellbeing in Group A during the intervention but not WLC. Group B then shows increased wellbeing during TLC, with Group A maintaining or slight decrease in “caregiver burden” or “anxiety” over time. With the planned 120 participants (60 per group), we will be able to detect small to medium effect sizes on the two outcomes with greater than 90% Power (see below). Intent-to-treat analyses (ITT) will be performed on non-completers using a terminal score for both “caregiver burden” and “anxiety” scores.

H2: Time-use satisfaction will be higher among the treatment group compared to those in control/waitlist (direct effect)

[figure not shown]

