Time-use satisfaction data will be collected daily using EMA, of short questions. First, did you have respite today? Then, if yes, how satisfied are you with your respite time-use? (1-

5) Did the respite time make you feel more positive/negative about your role as a caregiver? (1-5). These two items measure “experienced” and “evaluative” time-use measures, respectively, which have been theorized to be associated with the wellbeing outcomes (anxiety & caregiver burden). Aggregated averages of these two measures will be computed for specific time-periods (i.e., across the four-week interval spanning the primary data collection timepoints). The same MLM will test significance of time x intervention interaction on mean Time-use satisfaction following TLC intervention compared to WLC.

H3: Higher time-use satisfaction will be associated with lower burden & anxiety (direct effect)

Using the same MLM framework, we will examine if aggregate Time-Use Satisfaction (predictor) is associated with lower “caregiver burden” and “anxiety.” As an exploratory aim we will examine Time (β_1) immediately post intervention through follow up to determine maintenance, attenuation, or no change in Group A outcomes after TLC for wellbeing (anxiety & caregiver burden) and time-use satisfaction (experienced & evaluative time-use).

Figure 3: Time-use mediates TLC impact on Well Being

H4: Higher time-use satisfaction will mediate the effect of the intervention on burden and anxiety (direct & indirect effects)

Figure 3 displays our overall mediation model, whereby TLC intervention improves wellbeing by increasing Respite Time-Use Satisfaction. We hypothesize that “satisfaction with respite time-use” is the factor that links respite use with wellbeing outcomes such that TLC intervention leads to improvements in respite quality that in turn produces better outcomes over time.

Mediation analysis will be conducted as previously outlined for cross-sectional as longitudinal models.^{149, 138, 139} In its simplest form, mediation is represented by three linear equations

$$\text{Mediator (Time-Use)} = i1 + aX + e1 \quad (2)$$

$$Y (\text{Wellbeing}) = i2 + cX + e2 \quad [\text{without mediator}] \quad (3)$$

$$Y (\text{Wellbeing}) = i3 + c'X + bM + e2 \quad [\text{with mediator}] \quad (4)$$

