When substituting the Mediator M in equation 3 the indirect pathway by which the TLC intervention impacts wellbeing through time-use is represented by the product of coefficients $a \cdot b$. If significant, then mediation is present. If the direct pathway c in equation 3 becomes non-significant in equation 4 (c') when conditioning on the indirect pathway, then M is said to fully mediate the relationship between TLC and wellbeing. Importantly, in the models we will control for individual values of the wellbeing outcomes obtained before the start of the TLC intervention. The indirect pathway will be tested using the Sobel test that divides product-of-coefficients $a \cdot b$ by the first-order delta-method standard error of the indirect effect. This value is compared against a standard normal distribution to test for significance.¹⁴⁸ We will also consider additional statistical mediation tests that account for non-normality of the product of coefficients and/or bootstrapping methods for more accurate estimates.¹²¹

Although not stated as distinct hypotheses, we will conduct additional exploratory analyses to further explain for whom and how the intervention achieves its effect. These analyses will be guided by the following questions: Do variations in the receipt of the intervention modify these relationships? For example, do participants that report higher intervention feasibility (i.e., higher satisfaction and usability of the tool) or higher dosage (i.e., they accessed more of the intervention's features) show stronger treatment effects? This will be assessed by replacing the dichotomous intervention variable X (TLC vs. WLC) in equation 1 with measures indicating dosage or perceived feasibility. Similarly, we will explore whether individual characteristics or circumstances modify the relationship between intervention, time-use satisfaction, and wellbeing over time. Here, we will use biologic variables of gender and age as well as measures that capture changes in the context of the caregiving relationship as both control variables and interaction. Finally, we will explore whether treatment effects maintain, attenuate, or no-change once the intervention period ends. This will be assessed using a repeated-measures design using Group A's data from immediately post-intervention through the 8-week follow-up period.

Power and Sample Size

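### Equation 1 tests H1 through one pooled exposure term that the text does not define consistently; if its single time term is a straight line, a shared non-linear change can also bias the test

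*Combined protocol and SAP*

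**What the plan says.** The Analysis section announces the efficacy test: "The analysis to test for efficacy will specifically look at treatment x time interaction". The H2 text repeats it: "The same MLM will test significance of time x intervention interaction". Equation 1, which begins "Y_{ij} = [\beta_0 + \beta_1 T_j + \beta_2 X_{ij", has an intercept, one time coefficient, one exposure coefficient and no product term. Its random part includes an "individual-level slope of change over time". The definition of j calls it an indicator and lists the six surveys, without saying whether time enters as a number or as categories.

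X is described twice. Under equation 1 it "is the intervention status (pre-TLC or Post-TLC/Follow-up) at timepoint j". The exploratory paragraph speaks of "replacing the dichotomous intervention variable X (TLC vs. WLC) in equation 1".

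The start times differ by section. Procedures gives intensive coaching to Group #1 at week 1 and to Group #2 at week 9. Study Design has a 4-week orientation period, with TLC from week 4 in Group A and week 12 in Group B.

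Procedures also notes that "both group #1 and group #2 receive access to the TLC study tools from day 1", with a common orientation. The H1 text anticipates "no change during the run-in period".

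**The concern.** Two things have to be fixed before β2 can be estimated: the surveys at which X equals 1 in each group, and the form of the time term. The text settles neither.

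If X does not match what was delivered, exposed surveys are counted as unexposed or the reverse, and β2 no longer measures the effect of TLC. This needs no assumption about time trends.

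The second problem is conditional. A change shared by both groups cancels when the groups are compared survey by survey. It does not cancel around a straight line unless it is itself a straight line, or its shape happens to be balanced against the exposure pattern. Giving both groups the tools and orientation on day 1 is one route by which a shared early change could arise.

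**Working it through.** **Possible codings.** There are two schedules and two readings of X (exposed from the start of TLC, or only once TLC is complete).

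- Procedures, from start: on from T4 in A and T12 in B.
- Procedures, after completion: T8/T16.
- Study Design, from start: T8/T16.
- Study Design, after completion: T12/T20.

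That makes three distinct codings. The exploratory wording leans towards counting surveys during TLC as exposed; the definition under equation 1, read literally, leans the other way.

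**The plan's own figure.** Power and Sample Size gives N = 116 for more than 90% power by repeated-measures ANOVA. It cannot be reproduced uniquely, because no SD, correlation, number of measures or effect type is given. For example, within-between f = 0.125 with 4 measures and correlation 0.5 gives 0.904 at N = 116, and between-group f = 0.25 with 3 measures and correlation 0.5 gives 0.905. It therefore does not show which model was powered.

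**Inputs.** From the plan: six surveys, 60 per group. Assumed: baseline SD 1, ICC 0.5–0.7, random-slope variance adding 0–0.2 of baseline variance by week 20, two-sided 0.05, lower score better.

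**Formulae (no slope variance).** At each survey let m = (X_A + X_B)/2 and d = (X_A − X_B)/2. Let r be the residual of m from a straight line over the six surveys, R = Σr², λ = 6·ICC/(1 + 5·ICC) and D = Σd² − 6λ·(mean d)². For a shared change g:

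- linear time: bias = Σ(r·g)/(R + D), SE = √[(1 − ICC)/(120(R + D))];
- visit indicators: bias = 0, SE = √[(1 − ICC)/(120·D)].

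**Numbers at ICC 0.5.** λ = 3/3.5 = 0.857. In every coding the groups differ at two surveys, so D = 0.5 − 6 × 0.857/36 = 0.357.

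- T4/T12: r = (−0.167, 0.133, −0.067, 0.233, 0.033, −0.167), R = 0.133.
- T8/T16: r = (0.071, −0.157, 0.114, −0.114, 0.157, −0.071), R = 0.086.
- T12/T20: r = (0.167, −0.033, −0.233, 0.067, −0.133, 0.167), R = 0.133.

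For a shared 0.3 SD drop after T0, Σ(r·g) = 0.3 × r at T0, because r sums to zero:

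- T4/T12: −0.050/0.490 = −0.102 SD; SE 0.092; error Φ(−0.85) + Φ(−3.07) = 19.8%, favouring TLC.
- T8/T16: +0.0214/0.443 = +0.048 SD; SE 0.097; error 7.9%, against TLC.
- T12/T20: +0.102 SD; error 19.8%, against TLC.

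**Full variance range** (generalised least squares, linear time, no true effect; two-sided error):

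| Shared change, 0.3 SD | T4/T12 | T8/T16 | T12/T20 |
|---|---|---|---|
| Drop after T0 | 20–31%, for TLC | 8–10%, against | 20–32%, against |
| Step between T4 and T8 | 5.6–6.0% | 9–12%, for TLC | 14–22%, against |
| Smooth decline, half-life 4 weeks | 9.2–12.5%, for TLC | 5.1–5.2% | 10–14%, against |
| Quadratic levelling-off | 7–9%, for TLC | 5.0% | 7–9%, against |
| Straight line | 5.0% | 5.0% | 5.0% |

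At 0.2 SD the drop gives 11–16% (T4/T12) and 6–7% (T8/T16). At 0.1 SD it gives at most about 8% under any coding. Visit indicators give 5.0% in every cell.

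**Wrong coding of X.** Let the true constant effect follow m′ and d′. The fraction recovered is [Σ(r·m′) + Σ(d·d′) − 6λ·mean d·mean d′]/(R + D), or the same without the r and R terms for visit indicators. Coded T8/T16 with delivery T4/T12: (−0.050 + 0.250 − 0.143)/0.443 = 0.13, and 0.107/0.357 = 0.30. Over the variance range this is 10–14% and 27–31%. The reverse error gives 9–12% and 27–31%.

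**Pooling.** If the effect vanishes when the 8-week TLC period ends, T8/T16 coding gives (0.043 + 0.500)/0.443 = 1.23 with linear time and 0.500/0.357 = 1.40 with visit indicators. The ranges are 1.23–1.28 and 1.40–1.47 times the true effect.

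**The case against.** A reader might infer that the interaction is missing altogether. It is not: X switches on at different surveys in the two randomised groups, so β2 is already a restricted group-by-time contrast.

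A reader might also infer that the H1 test is known to be inflated in favour of TLC. The documents do not support that either. Calling j an indicator allows six categories, and a random slope can sit beside categorical fixed time; the shared-trend bias is then zero. The plan expects no run-in change and gives no size for one, and day-1 access is the only route it offers. Nothing in it explains a shared step between T4 and T8. Under T8/T16 a smooth decline is close to nominal, a quadratic levelling-off is exactly nominal, and an early drop works against TLC.

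For a Stage 1 pilot, linear time is partly a choice of precision over robustness. If there is no shared trend, visit indicators lower power for a true 0.25 SD from 73–91% to 64–84% (T8/T16) or from 77–93% to 63–84% (T4/T12). The design figure, not shown in the text available, may also tabulate exposure by survey.

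All of this stands, and it makes the trend argument conditional. It does not answer the coding of X: even a clear figure would leave two schedules and two wordings to align, and a mismatch removes most of the effect under either form of time.

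**Conclusion.** The point holds and should be fixed before analysis. The firm part is that X for the primary hypothesis cannot be built from the text without a choice among three codings; confusing T4/T12 with T8/T16 leaves roughly a tenth of a constant effect in β2 with linear time, and under a third with visit indicators.

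The conditional part is the shared-trend bias. It requires linear time and a non-linear change common to both groups, and its size rests on assumed variances and an assumed 0.3 SD. Its direction cannot be stated until X is settled: the same early drop favours TLC under T4/T12 and counts against it under the other two codings. Nor is large error confined to the Procedures schedule, since T12/T20 gives 20–32%.

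It would also be too strong to say that visit indicators repair everything. They remove the shared-trend bias but not the pooling, and they increase the overstatement of an effect that fades after TLC. The joining of burden and anxiety by both an and and an or in H1 is a separate matter to be raised on its own.

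**What to change.** 1. Reconcile the schedules in Procedures and Study Design and the two wordings of X, and add a table giving X for each group at each of the six surveys. This costs wording only.
2. State fixed time as five visit indicators in place of the single time term, keep all six surveys, and restate power for that model. The SE of β2 rises by 11–12% (T8/T16) or 17–18% (T4/T12). The effect detectable with 90% power at 120 participants moves from 0.23–0.32 SD to 0.28–0.35 SD across those two codings. No new data are needed.
3. Because visit indicators do not cure pooling, report as a supporting estimate the group difference at the last survey before Group B switches (T8 under Procedures, T12 under Study Design), from a group-by-visit model with a common T0 mean. This is closer to the immediate post-intervention change named in H1. It needs 0.42–0.54 SD for 90% power, so it should not be made the primary test.

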Respite, defined as time away from caregiving, has been identified as the most needed and desired service for family caregivers, especially the 16 million dementia caregivers who are faced with long term and demanding caregiving circumstances. Findings on the effectiveness of respite services have been mixed –how caregivers spend their respite time seems to be a key factor behind these inconsistent findings. We have developed a novel intervention called “Time for Living & Caring” (TLC) that shows promise in improving respite time-use and maintaining caregiver wellbeing. However, it relied on trained facilitators and up to 15-20 individual home visits or phone calls with each caregiver, limiting its scalability to real world practice. The purpose of this study is to redevelop the TLC intervention, in which AD/ADRD caregivers are taught strategies to assess and identify ways to spend upcoming periods of respite time, to a fully online, self-administered virtual coaching format, and then to pilot-test the new TLC intervention for feasibility and efficacy.

Aim 1 is to modify, adapt, and refine the existing intervention modules. This phase of the project utilizes a community-engaged design process where stakeholders (i.e., current or

former caregivers, diverse community leaders, respite providers) will work alongside the research, technical, and creative teams to develop and provide feedback on the TLC design, features, and prototypes.

Aim 2 is to conduct a pilot test with dementia caregivers who are currently using respite. This phase uses a full powered pilot sample (n=120) and a randomized waitlist control experimental design where participants are exposed to the redeveloped TLC intervention for 8 weeks and will provide assessments of daily respite use, respite time-use satisfaction, and wellbeing. These pilot data will be used to assess feasibility and to explore hypotheses regarding the potential efficacy of the intervention, as well as the mechanism (i.e., time-use satisfaction) underlying the intervention's effect on wellbeing. Wellbeing is measured with two primary outcome of anxiety and caregiver burden, both thought to be closely related and responsive to intervention's purpose.

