Participants are also asked to complete daily ecological momentary assessments (EMAs), in which they indicate if they used respite that day, and if so, their experienced and evaluative satisfaction with respite time-use. The daily EMAs will take about 1-2 minutes to complete as they are only 3 items (respite used [yes/no], and two items each measuring experienced and evaluative time-use satisfaction). The caregivers will be prompted weekly to complete their EMAs. Note: as mentioned above, all EMA data collection has been

integrated into the online version of the TLC intervention tools through a digital calendar, combining the TLC intervention with the collection of daily EMA.

Each questionnaire will take about 10-45 minutes to complete. The baseline and final questionnaire are significantly longer than the monthly questionnaires (i.e., 10 minutes versus 45 minutes). Questionnaires will include standardized fixed-choice and open-ended survey questions related to :

- demographic indicators
- caregiving context, and
- caregiver health and well-being (i.e., burden, anxiety, positive affect, global health).

The final questionnaire includes additional measures related to the participants' use of the TLC intervention tools. We will assess their perceptions of feasibility, usability, and acceptability of the online version of the TLC intervention. Other feasibility indicators such as login behavior, intervention protocol completion, and dosage will be imported in real-time directly from google analytics into the secure REDCap data base.

Procedures performed for research purposes only:

[figure not shown]
Statistical Methods, Data Analysis and Interpretation

STATISTICAL DESIGN & POWER

The overall project has three specific aims. This application relates to Aim 2, where which entails human subjects research.

Aim 2: Conduct a hypothesis driven pilot test of the TLC intervention with dementia caregivers

Statistical Design & Power - Aim 2

The purpose of Phase 2 is to conduct a fully-powered pilot study to measure feasibility and efficacy of the TLC intervention with a sample of dementia caregivers (n=120). This section describes the planned analyses to assess efficacy of the TLC intervention.

Study Design

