We assume clinically relevant small to medium effect sizes in the main outcomes of interest corresponding to 4-6.5 mean change on the total "caregiver burden" outcome and 1.0-1.4 mean change on the "anxiety" outcome. Power and sensitivity analysis were computed in GPower using RMANOVA finding a total sample of 116 would be sufficient to achieve

power of greater than 90% to detect these effect sizes. Therefore, we will aim to have a final sample size of 120 (60 in each sequence) with a 25% over-recruitment to account for study attrition providing a total sample size of 150.

Sample size and sensitivity analyses for mediation analyses are based on empirical estimates conducted by Fritz and MacKinnon (2007).¹²¹ Assuming medium effects for each of the two parts of the indirect pathways (i.e. TLC->Time-use and Time-use->Wellbeing) in Figure 3, a sample size of 75-120 will provide greater than 80% Power (Sobel148 medium-medium effects) at $p=0.05$.

Missing Data

We will explore missing data patterns in SPSS using the Missing Value Analysis tool. We will specify the pattern fixed effects and interactions utilizing Little's test for Missing Completely at Random. In keeping with an intent-to-treat standard and assuming maximum likelihood estimation, we will use all available data for analyses. It is not necessary to eliminate observations from participants who subsequently drop out, nor is it necessary to impute individual observations. Both practices can bias estimation and distort variability. The maximum likelihood estimates given the observed data points are the values most likely to have generated the complete ensemble of observed sample data under the assumed model. Systematic missingness (as determined by missing data patterns) may be included in our mixed effects model. Potentially non-ignorable missing data will be investigated using multiple imputation sensitivity analyses under a diverse set of covariate predictors. To minimize loss of scale scores due to missing items in a computed scale, we will prorate the respondent's score based on available items. If a respondent is missing more than 30% of the items in a computed score for the primary outcome variables, we will code the scale score as missing.

Note: feasibility is another primary outcome of the pilot test. Feasibility-related analyses are discussed at the end of this document, since the focus on feasibility and the analytic strategies to measure feasibility are shared across Aims 1, 2, and 3.

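### H1 pairs burden *and* anxiety, but its test is worded as one *or* the other, with no success or multiplicity rule; if *or* is the rule, the error rate exceeds its nominal level

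*Combined protocol and SAP*

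**What the plan says.** Two places in the combined protocol and SAP define the primary efficacy outcome. Purpose and Objectives, under Aim 2, says: "Wellbeing is measured with two primary outcome of anxiety and caregiver burden". The Measures section says: "The primary outcome is wellbeing, measured with two standardized scales indicating" burden and anxiety. Neither ranks the scales or combines them into one score.

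The Analysis section words H1 in two ways:

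- The hypothesis line: "Burden & anxiety will be lower among the treatment group compared to those in control/waitlist condition".
- The sentence on the primary test: "there will be significant change in “caregiver burden” or “anxiety” immediately post intervention".

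The H1 paragraph then claims that 120 participants suffice to "detect small to medium effect sizes on the two outcomes with greater than 90% Power". Power and Sample Size gives a separate effect range for each scale: "4-6.5 mean change on the total" burden score, and 1.0 to 1.4 on anxiety. It says a repeated-measures ANOVA calculation in GPower found 116 enough for power above 90%.

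No section gives H1 an alpha, a sidedness, a rule for when it is met, or a multiplicity adjustment. The only significance level in the plan, 0.05, belongs to the mediation sample size.

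The status of the efficacy test is also stated in two ways. Aim 2 will "explore hypotheses regarding the potential efficacy of the intervention", while Statistical Design & Power says the purpose is to "conduct a fully-powered pilot study to measure feasibility and efficacy of the TLC intervention".

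**The concern.** The two H1 sentences imply different trials. Under *and*, both scales must succeed. Under *or*, either one is enough, and two unadjusted chances to succeed raise the error rate above that of a single test.

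The practical risk is a split result, with one scale significant and the other not. The plan does not say whether H1 is then met, so the rule could be settled after the data are seen. The power claim has the same gap. With a separate effect range for each scale, it reads most naturally as power per outcome. It is then neither the power of an adjusted either-scale test nor the power to succeed on both, and the plan does not say which is meant.

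**Working it through.** **The plan's own figure.** The arithmetic 120 × 1.25 = 150 reproduces. The 116 cannot be reproduced uniquely, because the standardised effect size, standard deviations, alpha, number of measurements and correlation between measurements are not given. For the group-by-time interaction with f = 0.125 and a between-measurement correlation of 0.5, N = 116 gives 90.4% power with 4 measurements at alpha 0.05. It gives 90.3% with 5 measurements at alpha 0.025. The 116 therefore does not reveal which alpha was used.

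**Inputs.** From the documents: two primary scales, the two H1 wordings, and power above 90%. Assumed, not in the documents: one test per scale, two-sided 0.05 each (critical value 1.960), test statistics bivariate normal with correlation r. I show r = 0, 0.7 and 0.9. Aim 2 presents the two outcomes as closely linked, so the larger values of r are more plausible than 0.

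**Error under *or*, no effect on either scale.** Let B = P(Z1 > 1.96 and Z2 > 1.96), and let C be the probability that both are significant in opposite directions, one given way round.

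- False benefit = 0.025 + 0.025 − B.
- Significant change in either direction = 0.10 − 2B − 2C.

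| r | B | C | False benefit (one test: 2.5%) | Either direction (one test: 5%) |
|---|---|---|---|---|
| 0 | 0.00062 | 0.00062 | 4.94% | 9.75% |
| 0.7 | 0.00827 | about 0 | 4.17% | 8.3% |
| 0.9 | 0.01482 | about 0 | 3.52% | 7.0% |

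The either-direction column is the literal reading, since the test sentence speaks of change without a direction. The false-benefit column takes its direction from the H1 line.

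**Error under *and*.** With no effect on either scale, false benefit is B: 0.06% at r = 0 and 0.8% at r = 0.7. If one effect is real, the other scale must still pass its own test, so the rate is at most 2.5%. There is no inflation.

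**Power, if each test has exactly 90% at 0.05** (mean shift 1.960 + 1.282 = 3.242):

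- Both scales significant: 0.90 × 0.90 = 81.0% at r = 0; 84.7% at r = 0.7; 86.9% at r = 0.9.
- Split result = 2 × (0.90 − power for both): 18.0%, 10.6% and 6.2%.

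**Holm** (smaller p against 0.025, critical value 2.241; if significant, the other against 0.05):

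- False benefit with no effect on either scale: 2.48% at r = 0, 2.15% at r = 0.7, 1.81% at r = 0.9.
- Power for at least one scale when both effects are real: 97.5%, 91.6% and 88.5%.
- Power when only one effect is real: 84% at each r.

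**The case against.** The strongest reply is that *or* is loose listing. The same paragraph uses it again when describing the expected follow-up pattern, and elsewhere the plan pairs the scales: in the H1, H3 and H4 lines, in the power sentence and in the handling of non-completers. That stands. A reader might infer that the trial has an established false-positive rate near 10%, or near 5% for benefit. The documents do not support this. Neither H1 sentence is a formal decision rule, and the inflation disappears under *and*. The highest figures also need r = 0, which sits badly with the plan's own view that the outcomes are closely linked.

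Second, the 2.5% baseline needs a single directional test per scale. The Analysis section speaks of a treatment-by-time interaction over six assessments, while equation 1 has a single treatment coefficient. An interaction test with several degrees of freedom has no benefit tail. So the false-benefit figures hold only for a one-coefficient test.

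Third, this is a Stage 1 pilot that will explore hypotheses, and feasibility is another primary outcome. That lowers the weight. It does not remove the point, because the same plan calls Aim 2 hypothesis driven and fully powered, so H1 will be read as a test with a known error rate.

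A reader might also infer that the trial is underpowered. That is not shown: the plan claims more than 90%, so the 81–85% figures are scenarios at the floor of that claim.

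What survives these replies is that, under any reading of *or*, the plan does not say what a split result means.

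**Conclusion.** The point holds as a conditional one. The two H1 sentences disagree, both scales are primary and unranked, and nothing decides between an either-scale and a both-scales rule.

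- If *or* is the rule, with one unadjusted two-sided 0.05 test per scale, error in either direction is 7.0% to 9.75% instead of 5%, and false benefit 3.5% to 4.9% instead of 2.5% (r = 0.9 down to 0). The lower part of each range is the more plausible.
- If *and* is the rule, error is not inflated, but power for both scales is 81–85% (r = 0 to 0.7) when each test has exactly 90%.

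The alpha, the sidedness, one test per scale and the range of r are my assumptions. The weight is moderate to low, given the pilot stage and the partly exploratory aim.

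**What to change.** Use the same wording in the H1 line and the test sentence, and fix one rule before H1 is analysed.

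- **If either scale suffices:** H1 is met if burden or anxiety is lower at familywise two-sided 0.05 by Holm, with the smaller p tested at 0.025 and, if significant, the other at 0.05. Report estimates and 95% confidence intervals for both scales whatever the result.
- **If both are required:** H1 is met only if both are lower, each at two-sided 0.05.
- **If the exploratory reading is intended:** report both estimates with 95% confidence intervals and state that no single pass/fail claim will be made for H1.

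In each case, say that the power figure is per outcome if that is what was computed, give the GPower inputs, and restate power under the chosen rule.

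The cost is a few sentences; the sample stays at 120. If per-outcome power is exactly 90%, Holm has about 92% to 97% power for at least one scale when both effects are real (r = 0.7 to 0), and 84% when only one is. The both-scales rule has 81–85% (r = 0 to 0.7).
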